#### 9.2.3. Time to Flare Grade Reduction

The time to flare grade reduction is the time (in days) from initiation of study drug to the date that improvement (decrease) in anterior chamber flare grade of at least 1 unit was reached without being rescued (or discontinued due to the requirement for rescue therapy) at any time prior to Week 4. All rescued subjects and subjects who did not achieve treatment success will be right censored. Subjects who discontinue from the study for reasons other than rescue will be real-time censored. Event and censoring definitions are described in Table 7 below.

Missing anterior chamber flare grade will be imputed using the LOCF approach. A log-rank test will be performed for between group comparison. The Kaplan-Meier plot will be generated. Cox proportional hazards model with treatment group as a factor will be used to estimate the hazard ratio and corresponding 95% confidence interval.

Table 7: Event and Censoring for Time to Flare Grade Reduction Analysis

Situation	Event / Censored	Date of Event / Censoring
Flare grade reduction	Event	Date when the first AC flare grade with at least 1 grade decrease was achieved prior to Week 4 without being rescued at any time prior to Week 4
Flare grade reduction does not meet 1 grade reduction from baseline prior to or at Week 4	Censored	Date of Week 4
Rescued	Censored	Date of Week 4
Early discontinuation from study for reasons other than rescue	Censored	Date of study discontinuation or Week 4, whichever is the earlier

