#### 3.2.9. Visit Windows

Unless otherwise noted, any analysis using study visit will be mapped using the analysis window and presented as follows. If assessments are collected multiple times within a given study visit window, the result closest to the scheduled visit day will be used for summary presentations. If two measurements have the same distance to the expected day, the earlier value will be used. If a subject has multiple non-missing scheduled values on the same day, then the last one is used, as determined by the time collected, if available. If a scheduled assessment and an unscheduled or early termination assessment are collected within a given visit window, the value from the scheduled visit will be chosen over the value from the unscheduled visit. Unscheduled and early termination visits will be assigned to an unplanned study visit and visit number using the analysis windows described in Table 3 in case the scheduled visit was not performed. All assessments will be presented with the original study visit in the listings.

Visit	Target Day [1]	Window [1]
Day 4	4	Day 2 - Day 5
Week 1	8	Day 6 - Day 11
Week 2	15	Day 12 - Day 18
Week 3	22	Day 19 - Day 25
Week 4	29	Day 25+

 Days are determined based on the first dose of study drug.

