# 9.1. Analysis of Primary Efficacy Endpoint

The primary efficacy endpoint is the time to treatment success, where such time (in days) is defined as from initiation of study drug to when a cell count of 0 is achieved and maintained (without cell count increase to > 0) to Week 4 without being rescued (or discontinued due to the requirement for rescue therapy) at any time prior to Week 4. All rescued subjects and subjects who did not achieve treatment success will be right censored. Subjects who discontinue from the study for reasons other than rescue will be real-time censored. Event and censoring definitions are described in Table 4 below.

The primary analysis to test superiority of ADX-102 over vehicle is the stratified log-rank test, stratified for the baseline ACC grade, with missing data imputed using the last observation carried forward (LOCF) approach. The Kaplan-Meier method (Kaplan and Meier 1958) will be used to estimate the time to treatment success curve. The Cox proportional hazards model with treatment group as a factor, stratified by the baseline ACC grade, will be used to estimate the hazard ratio and corresponding 95% confidence interval.

Table 4: Event and Censoring for Time to Treatment Success Analysis

Situation	Event / Censored	Date of Event / Censoring
Treatment success	Event	Date when the first cell count of 0 is achieved prior to or at Week 4 and maintained (without cell count increase to > 0) to Week 4 without being rescued any time prior to Week 4
Cell count greater than 0 at Week 4	Censored	Date of Week 4
Rescued	Censored	Date of Week 4
Early discontinuation from study for reasons other than rescue	Censored	Date of study discontinuation or Week 4, whichever is the earlier

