# 9.2. Analysis of Secondary Efficacy Endpoints

#### 9.2.1. Time to Cell Grade Reduction

The time to cell grade reduction is defined as the time (in days) from initiation of study drug to the date that improvement (decrease) from baseline in ACC grade of at least 1 grade was achieved without being rescued (or discontinued due to the requirement for rescue therapy) at any time prior to Week 4. All rescued subjects and subjects who did not achieve treatment success will be right censored. Subjects who discontinue from the study for reasons other than rescue will be real-time censored. Event and censoring definitions are described in Table 5 below.

Missing ACC grade will be imputed using the LOCF approach. A log-rank test stratified by the baseline ACC grade will be performed for between-group comparison. The Kaplan-Meier plot will be generated. The Cox proportional hazards model, with treatment group as a factor and

stratified by the baseline ACC grade, will be used to estimate the hazard ratio and corresponding 95% confidence interval.

Table 5: Event and Censoring for Time to Cell Grade Reduction Analysis

Situation	Event / Censored	Date of Event / Censoring
Cell grade reduction	Event	Date when the first ACC grade with at least 1 grade decrease from baseline was achieved without being rescued at any time prior to Week 4
Cell grade reduction does not meet 1 grade reduction from baseline prior to or at Week 4	Censored	Date of Week 4
Rescued	Censored	Date of Week 4
Early discontinuation from study for reasons other than rescue	Censored	Date of study discontinuation or Week 4, whichever is the earlier

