## 9.2.2. Time to Flare Treatment Success

The time to flare treatment success is defined as the time (in days) from initiation of study drug to the date that the anterior chamber flare grade reached 0 and maintained (without flare grade increase to > 0) to Week 4 without being rescued (or discontinued due to the requirement for rescue therapy) at any time prior to Week 4. All rescued subjects and subjects who did not achieve treatment success will be right censored. Subjects who discontinue from the study for reasons other than rescue will be real-time censored. Event and censoring definitions are described in Table 6 below.

Missing anterior chamber flare grade will be imputed using the LOCF approach. A log-rank test will be performed for between group comparison. The Kaplan-Meier plot will be generated. The Cox proportional hazards model with treatment group as a factor will be used to estimate the hazard ratio and corresponding 95% confidence interval.

Table 6: Event and Censoring for Time to Flare Treatment Success Analysis

Situation	Event / Censored	Date of Event / Censoring
Flare treatment success	Event	Date when the first anterior chamber flare grade of 0 is achieved prior to or at Week 4 and maintained (without flare grade increase to > 0) to Week 4 without being rescued any time prior to Week 4
Anterior chamber flare grade greater than 0 at Week 4	Censored	Date of Week 4
Rescued	Censored	Date of Week 4
Early discontinuation from study for reasons other than rescue	Censored	Date of study discontinuation or Week 4, whichever is the earlier

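### SAP Table 7 has no row for a flare reduction first seen at the Week 4 visit; the Day 25 overlap in the visit windows is a minor companion correction

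*SAP*

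**What the plan says.** SAP Section 9.2.3 defines time to flare grade reduction in prose as running from first study drug to the date that "improvement (decrease) in anterior chamber flare grade of at least 1 unit was reached without being rescued". In that sentence the limit of before Week 4 attaches to rescue, not to the reduction. The prose then hands the rule to the table: "Event and censoring definitions are described in Table 7 below".

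Table 7 has four rows. The event row, labelled as flare grade reduction, gives the date as "Date when the first AC flare grade with at least 1 grade decrease was achieved prior to Week 4 without being rescued". The no-reduction row censors at Week 4 when "Flare grade reduction does not meet 1 grade reduction from baseline prior to or at Week 4". The other two rows cover rescue and early discontinuation for other reasons.

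The sister tables are worded differently:
- Table 4 (primary endpoint): "Date when the first cell count of 0 is achieved prior to or at Week 4 and maintained".
- Table 6 (flare treatment success): "Date when the first anterior chamber flare grade of 0 is achieved prior to or at Week 4 and maintained".
- Table 5 (cell grade reduction, the closest analogue): before Week 4 limits rescue only, and nothing limits when the reduction may occur.

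On visit windows, SAP Section 3.2.9 gives Week 3 as Days 19 to 25 and Week 4 as Day 25 onward. It also states: "Unscheduled and early termination visits will be assigned to an unplanned study visit and visit number using the analysis windows described in Table 3", with the condition that the scheduled visit was not performed.

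**The concern.** An event-and-censoring table should place every subject in exactly one row. Table 7's event row stops short of Week 4, but its no-reduction row looks through Week 4, so the two do not meet. Week 4 is one of five post-baseline slit lamp visits, so a first reduction seen there is an ordinary outcome.

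One programmer following the event row literally would not count such a subject as an event. Another following the prose would. The two would report different event counts, log-rank p-values and hazard ratios for a listed secondary endpoint, and the choice would be settled only at programming.

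The Day 25 overlap is a smaller matter of the same kind: one study day carries two visit labels.

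**Working it through.** No stated figure is at issue here, so the check is one of coverage.

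**Table 7.** Take a subject who completes the study without rescue, so that the rescue and discontinuation rows do not apply. Three outcomes are possible:

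| First one-grade flare decrease | Event row as written | No-reduction row | Rows met |
|---|---|---|---|
| Before Week 4 | met | not met | 1 (event) |
| At Week 4 | not met | not met | 0 |
| Never by Week 4 | not met | met | 1 (censored) |

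If the event row also admits Week 4, as Tables 4 and 6 do, the middle line becomes an event and each outcome meets exactly one row.

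LOCF does not close the gap. A carried-forward value repeats an earlier one, so a reduction first appearing at Week 4 must come from an observed Week 4 examination.

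**Visit windows.** The windows are Days 2–5, 6–11, 12–18, 19–25, and 25 onward. Checking every day from Day 2 on, Day 25 is the only day in two windows, and no day is in none.
- The midpoint of the Week 3 and Week 4 targets is (22 + 29) / 2 = 25.5, so a midpoint split ends Week 3 at Day 25 and starts Week 4 at Day 26. The two preceding boundaries follow the same pattern: (8 + 15) / 2 = 11.5 and (15 + 22) / 2 = 18.5.
- Day 25 is 25 − 22 = 3 days from the Week 3 target and 29 − 25 = 4 days from the Week 4 target.
- The protocol visit windows are 22 ± 2 = Days 20–24 and 29 ± 3 = Days 26–32. Day 25 is in neither, so only off-schedule examinations can fall on it.

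**Does the overlap reach the primary endpoint?** Consider an unscheduled or early-termination examination on Day 25 with a cell count of 0.
- Week 3 performed, Week 4 not: the scheduled value holds Week 3, and the Day 25 value can fill only Week 4.
- Week 4 performed, Week 3 not: the Day 25 value can fill only Week 3.
- Neither performed: the label is ambiguous. Labelled Week 3, the 0 is carried to Week 4 by LOCF. Labelled Week 4, it is 0 there. The Week 4 value is the same.

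Table 4's rows for rescue and early discontinuation do not depend on the window label.

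**Interaction.** A flare reduction first seen on Day 25 is a Table 7 event if labelled Week 3 and fits no row if labelled Week 4. Correcting the Table 7 event row removes this.

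**The case against.** The strongest reply is that the intent is plain. The row label sends a flare grade reduction to the event category, the prose does not limit when the reduction occurs, and the censoring row expressly excludes a subject who reduces at Week 4. The limiting phrase sits only in the date cell. The endpoint is secondary, and SAP Section 3.2.3 reserves inference for a single primary endpoint.

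All of this is right about intent and importance. It does not remove the defect, because the prose defers to Table 7 for the event definition and the date cell is what would be programmed.

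Three stronger readings are tempting, and the documents do not support them:
- *Genuine improvements are censored and lost.* No row of Table 7 censors these subjects. They are unclassified.
- *The affected share can be computed from the hazards in SAP Section 2.3.6.* Those hazards (0.2672 and 0.1098) are for time to treatment success, meaning a sustained cell count of 0, and are given without a time unit. They say nothing about a first one-grade flare decrease.
- *The Day 25 overlap can change the primary outcome.* The condition that the scheduled visit was not performed settles most cases, and in the remaining one LOCF gives the same Week 4 value.

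**Conclusion.** The Table 7 event row is wrong as written. It should be corrected before database lock and unmasking. A non-rescued completer with a first one-grade flare decrease at Week 4 meets no row, and a literal reading of the event row omits that event from the endpoint's log-rank test and hazard ratio.

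The effect is confined to this one secondary endpoint. For each affected subject the question is whether the Week 4 date counts as an event. Neither the number of such subjects nor the direction of any effect on the treatment comparison can be derived. Table 4 includes Week 4, so the primary endpoint is not affected.

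The Day 25 overlap is real but minor. It concerns only off-schedule examinations, and no effect on the primary outcome is shown. Where both scheduled visits were missed, it leaves open which by-visit summary receives the value.

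**What to change.** In the Table 7 event row, change the limit on the reduction from *prior to Week 4* to *prior to or at Week 4*, matching Tables 4 and 6. Leave the separate limit on rescue as it stands. This is a one-phrase edit with no analytical cost.

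In the Section 3.2.9 window table, make Weeks 3 and 4 disjoint, for example by starting Week 4 at Day 26. That agrees with the midpoint split and with the protocol's Day 26–32 visit window. It has a small cost: a Day 25 examination after a performed Week 3 visit would then lose to the scheduled Week 3 value and could no longer serve as the Week 4 value. The team should accept that knowingly when making the edit.

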#### 2.3.6. Sample Size and Power

Based on the Phase 2 clinical trial results, a true hazard rate of 0.2672 and 0.1098 is assumed for the time to treatment success in ADX-102 and vehicle group, respectively. With approximately 53% censoring rate, a sample size of 90 subjects (45 per group) yields 82% power to detect the superiority of ADX-102 over vehicle group with the use of a 2-sided log-rank test and a type I error of 0.05. Under the same assumption, a sample size of 120 subjects (60 per group) will provides 91% power.

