# 3.2.8. Study Baseline and Study Day

For purposes of analysis the baseline value is defined as the last non-missing value obtained prior to initiation of study drug, nominally the Screening Visit. Measurements that are obtained after the first dose of study drug will be considered post-baseline values. If a measurement of a variable is not made on a given subject prior to the first dose of study drug, then that subject will be considered not to have a baseline value for that parameter. Change from baseline is defined as non-missing post-baseline assessment value minus baseline assessment value.

Study day for events on or after the date of the first dose will be defined as the number of days from the date of the first dose of study drug, plus 1 day, so that the date of the first dose will be defined as Day 1. For events before the date of the first dose, study day will be calculated as the difference in days between the date of the first dose and the date of interest. Thus, the day before the date of the first dose will be defined as Day -1.

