# 9.3.1. Slit Lamp External Eye Exam and Biomicroscopy

The examination of anterior uveitis is performed on both eyes (study and non-study eye) by external examination and biomicroscopy using a slit lamp. Slit lamp examination will be completed at Day 1 (Screening), Day 4, Week 1, Week 2, Week 3 and Week 4.

Changes from baseline in signs and symptoms of anterior uveitis which include Anterior Chamber Cell Grade, Anterior Chamber Flare Grade, Limbal Injection, Hypopyon, Peripheral Anterior Synechiae, Posterior Synechiae, Keratic Precipitates and Eyelid are the interest of treatment efficacy.

Descriptive summaries of the observed exam results at each scheduled visit as well as the change from baseline at each post-baseline visit will be presented for both eyes (study and non-study eye), without imputation. The numerical value of the exam result categories will be used in the summaries. The higher score representing more severe symptoms.

Number and percentage of subjects with Eyelid categories of Normal or Abnormal as well as the categorical shift from baseline at each post-baseline visit will also be summarized. The percentages will be calculated based on the number of subjects at each visit in each treatment group of the ITT analysis set. The percentages on the shift will be calculated based on the number of subjects with both baseline and post-baseline values.

In addition to the descriptive summary, the change from baseline in anterior chamber cell grade and flare grade will be analyzed using Mixed effect Model Repeat Measurement (MMRM) method. The MMRM model will include the fixed categorical effects of treatment, random effect visit, and treatment-by-visit interaction, as well as continuous fixed covariates of baseline score. An unstructured covariance structure of random effect will be used for modeling the within-subject errors. If the unstructured covariance structure matrix results in a lack of convergence, the model will be fit using covariance matrices of the following order until convergence is met:

- Heterogeneous Toeplitz
- Heterogeneous First-order autoregressive
- Toeplitz
- First-order autoregressive

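### Time to flare grade reduction (SAP Table 7) keeps study eyes with no baseline flare at risk as certain non-events, which costs some power, and the table's event row needs correcting

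*SAP*

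**What the plan says.** Protocol 6.1 requires anterior chamber cells of Grade 1+ to 3+ in the study eye. The entry summary in SAP 2.3.1 names cells, IOP and visual acuity. Neither sets a minimum flare grade. Exclusions 12 and 13 and the Appendix 1 grading scale are not visible.

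SAP 9 runs all efficacy analyses on the ITT set. SAP 9.2.3 adds no baseline-flare condition, stratum or covariate. The relevant rows are:

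- **Table 7, event:** "Date when the first AC flare grade with at least 1 grade decrease was achieved prior to Week 4 without being rescued".
- **Table 7, censored at the date of Week 4:** "Flare grade reduction does not meet 1 grade reduction from baseline prior to or at Week 4".
- **Table 5 (cell grade reduction), event:** "Date when the first ACC grade with at least 1 grade decrease from baseline was achieved".
- **Table 6 (flare treatment success), event:** "Date when the first anterior chamber flare grade of 0 is achieved prior to or at Week 4 and maintained".

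SAP 3.2.1 and SAP 9 make the log-rank test stratified by baseline ACC grade the primary method for time-to-event endpoints, while 9.2.2 and 9.2.3 say only that a log-rank test is used. SAP 3.2.3 plans no multiplicity adjustment. No power is stated for either flare endpoint.

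**The concern.** Every eligible study eye starts with cells, so each can lose a cell grade. Table 7 applies the same event structure to flare, where no visible criterion ensures there is anything to lose. An eye at flare 0 is a certain non-event. It stays in the risk set at every event time unless the subject leaves early for a reason other than rescue. Such subjects carry no information on flare reduction and pull the two arms together.

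The wording of Table 7 is a separate problem that does not depend on how many such subjects enrol:

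- The event row omits the baseline reference, which its own censoring row and Table 5 both contain. Read literally, a rise from 0 followed by a fall could count as an event.
- The event row stops before Week 4, while the censoring row runs up to and including it. A reduction first seen at the Week 4 visit fits neither row.

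**Working it through.** **Inputs from the SAP (2.3.6).** "a true hazard rate of 0.2672 and 0.1098 is assumed for the time to treatment success" (ADX-102 and vehicle respectively), about 53% censoring, two-sided 5% log-rank test, 60 per arm.

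**Assumptions.** The documents give no flare-0 share, flare hazards or expected rescue rates. The primary-endpoint hazards are borrowed and read as per week, since the SAP gives no time unit. The shares and rescue rates below are illustrations.

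**1. The plan's own figure.** HR = 0.1098/0.2672 = 0.411, and ln HR = −0.889. Schoenfeld power = Φ(√(d/4) × |ln HR| − 1.96), where d is the number of events.

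- 90 subjects: d = 90 × 0.47 = 42.3, giving 82.4% (SAP: 82%).
- 120 subjects: d = 120 × 0.47 = 56.4, giving 91.6% (SAP: 91%).

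Both reproduce. The per-week reading is plausible: 1 − exp(−4 × 0.2672) = 65.7% and 1 − exp(−4 × 0.1098) = 35.5% have the event by Week 4. That leaves about 49% censored on average, near the stated 53%.

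**2. Event rates with a flare-0 share q.** Without rescue, each arm's rate is multiplied by (1 − q). At q = 20%: 0.8 × 65.7% = 52.5% and 0.8 × 35.5% = 28.4%.

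**3. Power for Table 7.** Simulated trials of 60 per arm, with exponential times observed at Days 4, 8, 15, 22 and 29, and an unstratified log-rank test. Baseline-0 and rescued subjects are non-events censored at Day 29. There were 20,000 trials per cell (Monte Carlo standard error under 0.4 point). Rescue is given as active/vehicle.

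| Flare-0 share | Rescue | Full ITT | Baseline flare ≥ 1 |
|---|---|---|---|
| 5% | none | 90% | 91% |
| 10% | none | 87% | 90% |
| 20% | none | 79% | 86% |
| 30% | none | 70% | 81% |
| 20% | 30/30% | 56% | 60% |
| 20% | 20/40% | 87% | 90% |
| 20% | 30/55% | 88% | 91% |

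Across independent runs and these rescue patterns, the loss is about 1 to 3 points at 10%, 3 to 8 at 20% and 5 to 12 at 30%. With no flare effect and no rescue, rejection is about 5% in both versions. Hazards are a further uncertainty: at 20% without rescue, halving them gives 61% against 65%, and doubling them 84% against 96%.

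**4. Does stratifying by ACC grade remove the loss?** Assume 50/33/17% of subjects in ACC 1+/2+/3+. If flare 0 is unrelated to ACC grade, stratified power at a 20% share is 79.9% against 86.6%, the same gap. If all flare-0 eyes are in ACC 1+, an extreme case, the stratified gap is 4.6 points at 20% and 5.5 at 30%, against 6.4 and 10.9 unstratified.

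**5. Does the Week 4 wording matter for the gap?** Leaving out reductions first seen at Day 29 lowers power in both versions but leaves a gap of about 6 points at a 20% share without rescue.

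**6. Table 6, for contrast.** An eye at flare 0 that stays there without rescue has its event at the first visit. Flare-success power at a 20% share, full ITT against baseline flare of at least 1, is 73% vs 86% (no rescue), 45% vs 61% (30/30%), 89% vs 91% (20/40%) and 91% vs 91% (30/55%). At a 30% share with 30/55% rescue it is 89% vs 87%, so restriction loses power there.

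**The case against.** The strongest objection is that the premise is not shown. Part of the exclusion list and the grading scale cannot be read, and nothing in the documents favours a 20% or 30% flare-0 share over one near zero. At 5% the loss is about 1 point. The borrowed hazards belong to another endpoint. Rescue is built into this trial, and with rescue included the loss is smaller. All of this stands, and it is why the size is given as a range tied to assumptions.

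It can also be said that full ITT is the stated efficacy population, so its event rates are correct for that population and restriction asks a narrower question. That is fair, and it is a reason to keep the full-ITT version as supportive. Flare change is also analysed by MMRM with "continuous fixed covariates of baseline score" (SAP 9.3.1), which limits the consequence but does not repair the Table 7 comparison.

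A reader might infer that Table 6 needs the same restriction. The documents do not support that. Restriction there can gain or lose power depending on rescue, and it removes subjects who start at 0 and develop flare, an outcome that Table 6 is designed to count. A reader might also blame flare-0 eyes for spurious flare-success findings. With no flare effect and 30/55% rescue, simulated rejection is 43% in full ITT and 29% restricted at a 20% share. But it is already 35% with no flare-0 eyes, and the hazard ratio barely moves (1.67 and 1.65). The cause is the rescue rule, which covers everyone: "All rescued subjects and subjects who did not achieve treatment success will be right censored".

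**Conclusion.** The point holds for Table 7. Any study eye enrolled at flare 0 is a certain non-event that stays at risk, which lowers power without inflating type I error. The power loss depends on three things the documents do not give: the flare-0 share, the flare hazards and the rescue rates. Under the borrowed hazards it is modest at a 10% share and noticeable at 30%. Stratifying by baseline ACC grade does not remove it, though it shrinks somewhat if flare 0 is concentrated in ACC 1+.

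The consequence is confined to one secondary endpoint with no multiplicity-adjusted claim, and the primary analysis is unaffected. The documents do not show that many subjects enter at flare 0, and they do not support a claim of bias in favour of ADX-102. The Table 7 wording conflict stands whatever the share is.

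**What to change.** Before unmasking:

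1. In SAP 9.2.3, make the main Table 7 analysis the ITT subjects with study-eye baseline flare of at least 1, and keep the planned full-ITT analysis as supportive. Equivalently, keep full ITT and add baseline flare (0 against at least 1) as a stratum. The flare-0 stratum has no events, so it adds nothing to the log-rank statistic and the result is the same.
2. Correct the Table 7 event row so that the one-grade decrease is measured from baseline and may occur before or at Week 4, matching the censoring row.
3. Report by arm the number of study eyes at baseline flare 0.
4. For flare treatment success (Table 6), keep the full-ITT analysis as planned and add the baseline-flare-of-at-least-1 subset only as a supportive analysis.

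The cost is a few sentences. The slit lamp exam is already done at Screening, and the condition uses a pre-dose value, so the randomised comparison is preserved. The downside is fewer subjects in one secondary analysis: 0.8 × 120 = 96 at a 20% share. If nobody enrols at flare 0, the restriction changes nothing.
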